19.1.6 Sample Size Justification

The feasibility study aims to register 60 patients over a three-month period. There is no statistical basis for this sample size; 60 was chosen as a logistically sensible number deemed sufficient to inform the RCT.

19.2 Randomised Controlled Trial

19.2.1 Definition of Outcome Measures

19.2.1.1 Primary outcome measures

The primary objective of the statistical analysis is to compare the two treatment arms in terms of the following co-primary outcome measures:

- GHSS from the EORTC QLQ C30 longitudinal questionnaire at three months post randomisation. GHSS is a descriptive measure of quality of life ranging from 0 (the worst score) to 100 (the best score)
- QAS over six months, combining the utility measure from the EQ5D questionnaire with survival time. QAS over six months will be calculated using the area under the curve formed by the longitudinal measures of the utility scores from EQ-5D-5L within six months, with all values from death onwards represented by 0 and imputation used to complete the curves where data are missing. Values will range from 3.54 (the worst score, i.e. full survival at the worst QoL valued at -0.59) to 6.0 (the best score, i.e. full survival with perfect QoL).

19.2.1.2 Secondary outcome measures

A secondary objective will be to compare the arms of SPARC sub-randomisation in the early palliative care group to see if HNA as an intervention is associated with better outcomes.

Other secondary outcome measures are defined as:

Overall survival: defined as the time from randomisation to death (due to any cause) or to date last seen for those not known to have died.

Anxiety/depression: will be measured using the HADS questionnaire and scored as per the HADS algorithm.

Pain: based on the EORTC QLQ-C30 and -LC13 questionnaire pain domains.

Health Economics; Cost Effectiveness and Resource Use

- Days spent in hospital/hospice: obtained from patient records. Duration defined as time from admission to discharge.
- Use, or not, of medical interventions in last month of life: details of further interventions administered during the last month of life will be obtained from patient records. The patient subgroup will be defined as those for which death was observed.
- **ITU admission:** the number of patients admitted, the frequency and duration of visits will be obtained from patient records. Duration is defined as the time from admission to discharge from intensive treatment unit.
- Use of CPR: obtained from patient records.

QoL: Health related quality of life will be assessed using EQ-5D-5L and EORTC QLQ C30/LC13/BM22 instruments. The instruments will be scored as per the associated algorithm.

Memory and cognitive ability: will be assessed for consenting participants using administration of the MoCA. The instruments will be scored as per the associated algorithm.

mGPS: will be assessed at baseline, 3 and 6 months. The instruments will be scored as per the associated algorithm.

Secondary outcomes pertaining to family care-givers include:

Health Survey: assessed using the SF-12®. The instruments will be scored as per the associated algorithm.

Satisfaction with participant's end of life care: assessed using the CODE™ instrument and scored as per the associated algorithms.

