2.2.2 Randomised Controlled Trial Outcome Measures

The primary objective is to compare the two treatment arms in terms of the two co-primary outcome measures:

- (i) Global Health Status Score (GHSS) at three months post randomisation, and
- (ii) Quality-Adjusted Survival time (QAS) over six months

Secondary outcome measures:

- Overall survival
- Anxiety/depression
- Pain
- Quality of Life
- Cost-effectiveness
- Resource use
 - Days spent in hospital/hospice
 - Admission to an Intensive Therapy Unit (ITU)
 - Use of medical interventions in last month of life (see Appendix 1 for definitions)
 - Use of cardio-pulmonary resuscitation (CPR)
 - Compare the arms of SPARC sub-randomisation in the early palliative care group to see if HNA as an intervention is associated with better outcomes

The following will be measured from trial entry at each clinic visit the patient attends until the end of the trial or death:

- Health related quality of life using EQ-5D-5L and European Organisation for Research and Treatment of Cancer (EORTC) QLQ C30/LC13/BM22
- Hospital Anxiety and Depression Scale (HADS)
- HNA using SPARC (see Appendix 2)
- Modified Glasgow Prognostic Score (mGPS) (see Appendix 3)
- Nurse-rated and patient-rated ECOG
- Montreal Cognitive Assessment scale (MoCA) (see Appendix 4)

Additionally carers will receive:

- Short form-12® (SF-12®) health related quality of life questionnaire
- Family caregiver satisfaction of palliative care services questionnaire (FAMCARE-2)
- The CODE™ instrument

The modified Glasgow Prognostic Score will be used primarily as a prognostic and stratification measure at baseline. It will be repeated again at the key primary end-points of three months and six months to test for its utility as a prognostic score later in the disease ^{[7],[8]}.

In order to control for effects of co-morbidity on patients' physical condition and holistic needs, the Scottish Lung Cancer Co-Morbidity Index (see Appendix 5) will also be used at baseline^[9]. Neither this co-morbidity index nor the mGPS are outcome measures but do represent important potential antecedent variables which could influence symptoms and other holistic needs as well as survival, so will be used in the statistical analysis to help explain variations in the patients' outcomes.

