3.2 Randomised Controlled Trial

Stage two will be a non-blinded, prospective randomised controlled interventional trial in which consenting patients with newly diagnosed stage IV NSCLC will be randomly allocated to either standard oncological/respiratory care alone, where the patient could be later referred to palliative care specialists, or early referral to local palliative care services (i.e. within two to four weeks of diagnosis) as well as local standard oncology/respiratory medical treatment and follow-up.

Patients randomised to the early SPC referral arm will be further randomised into two groups where half the patients will be asked to complete a SPARC questionnaire to assess their wider holistic needs.

Patients will be entered into the trial over a three year period and will be followed up for three years or until death.

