19.2.2.2 Secondary Outcome Measures

The following measures will be reported by treatment arm:

Overall survival: A Kaplan Meier plot of overall survival will be reported along with hazard ratio and median survival (both with 95% CI).

Anxiety/depression: The average change in HADS score from baseline to six months will be compared using a t-test (or non-parametric alternative). The mean area under curve will also be compared using a t-test.

Pain: The average change in pain domain score from baseline to six months will be compared using a t-test (or non-parametric alternative). The mean area under curve will also be compared using a t-test.

Cost Effectiveness:

- Days spent in hospital/hospice Mean (95% CI) stay and overall stay duration and frequency
 of hospital/hospice say durations will be compared using a t-test (or non-parametric alternative).
 The number of patients admitted but not discharged will be reported. The proportion of patients
 spending time in hospital/hospice will be reported.
- Use, or not, of medical interventions in last month of life A line-listing of medical interventions including, where applicable, intervention type, dose, duration and other pertinent metrics. The period over which these interventions are to be observed will also be reported (some may not have been followed for a month).

ITU admission: The number of ITU visits, and the number of patients making those visits along with the mean (95% CI) length of each visit, and the mean (95% CI) of patients overall ITU duration.

Use of CPR: The proportion of patients requiring CPR and the average number of resuscitations required per patient will be reported.

For each of the questionnaire based outcome measures the mean (sd) score will be reported by visit.

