19.2.5.1 Global Health Status Score

Assuming a median survival time in these patients of six months and an exponential distribution, it is expected that 70% of randomised patients will be alive at three months. Experience in the BTOG2 trial shows that we would expect high compliance in these remaining patients, so we assume a further 5% dropout for reasons other than death, giving a total loss of 35% of randomised patients. From literature, GHSS in patients with metastatic NSCLC is 58.8 with standard deviation of 23 points and data from the stage IV patients in the BTOG2 trial shows similar values with a mean GHSS at baseline of 61.5 and standard deviation (SD) of 23. A difference of seven points between treatment groups at three months, which is a standardised effect size of 0.3, is considered to be realistic and clinically relevant. Assuming a 5% two-sided significance level and 80% power the analysis requires a total of 342 patients to detect this level of difference and thus 525 randomised patients. For 90% power the analysis requires a total of 456 patients and thus 700 randomised patients.

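### Hospital, hospice and ITU stays are timed only to discharge, so a stay that ends in death has no defined duration

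*Protocol*

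**What the plan says.** Section 2.2.2 lists "Days spent in hospital/hospice" under resource use, among the secondary outcomes of the randomised stage. ITU admission is listed there too.

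Section 19.2.1.2 gives the definitions. For hospital and hospice: "Duration defined as time from admission to discharge". For ITU: "Duration is defined as the time from admission to discharge from intensive treatment unit". Neither names death as an end of stay.

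Section 19.2.2.2 gives the analysis. For hospital and hospice it plans "Mean (95% CI) stay and overall stay duration and frequency", with durations compared by t-test or a non-parametric alternative, and then states "The number of patients admitted but not discharged will be reported". For ITU it plans counts of visits and patients, the mean length of a visit and "the mean (95% CI) of patients overall ITU duration". It names no between-arm test for ITU and no count of visits without a discharge.

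On mortality, section 19.2.5.1 works from "Assuming a median survival time in these patients of six months and an exponential distribution", and section 3.2 says "Patients will be entered into the trial over a three year period and will be followed up for three years or until death". Section 7.2.4 asks sites to obtain the date of death and where the patient was at the time.

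**The concern.** A patient who dies in hospital, hospice or ITU is never discharged. Under the written definition the last stay has a start and no end, so it cannot contribute a number of days. The separate hospital/hospice count of patients without a discharge fits that reading: such patients are tallied, and no length is assigned to their stay.

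In a population with short survival this affects many patients. The days lost are those immediately before death, in a trial whose commissioned question (section 2.1) names end-of-life care and whose objectives (section 2.1.3) ask whether early referral shifts resource use out of hospitals. Total days per patient would be too low in both arms. The mean length of a single stay would also be off, downwards if terminal stays are longer than the others. If the arms differ in how often patients die in hospital or hospice, or in how long the final stay lasts, the difference between arms would be wrong as well.

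**Working it through.** The protocol states no figure for this outcome, so there is none to reproduce. The check is of what the definition does, followed by an illustration of size.

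**Step 1: is a terminal stay closed anywhere?**

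| Place | Hospital/hospice | ITU |
|---|---|---|
| Definition, 19.2.1.2 | ends at discharge | ends at ITU discharge |
| Analysis, 19.2.2.2 | mean and overall duration, t-test or non-parametric alternative | mean per visit and overall per patient, no test named |
| Stays without discharge, 19.2.2.2 | number of patients reported | not mentioned |
| Death as end of stay | not stated | not stated |

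By contrast, section 19.2.1.1 does deal with death for quality-adjusted survival, by setting utility to zero from death onwards.

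**Step 2: how many patients die?** With exponential survival and a six-month median (19.2.5.1), the proportion dead by month t is 1 − 0.5^(t/6).

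- At 6 months: 1 − 0.5 = 50%.
- At 36 months: 1 − 0.5^6 = 98%.
- At the final analysis, timed to the last patient's six-month data (19.2.4), with three-year accrual assumed uniform, follow-up runs from 6 to 42 months. With L = ln 2 / 6, the proportion alive is (0.5 − 0.5^7) / (36 × L) = 0.492 / 4.159 = 0.118, so about 88% have died.

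**Step 3: days omitted per randomised patient over six months.**
Omitted days = P(death) × share of deaths in hospital or hospice × mean terminal stay.

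The last two inputs are not in the protocol. Assumed ranges: share 30% to 70%, terminal stay 5 to 15 days.

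- Low: 0.50 × 0.30 × 5 = 0.75 days.
- High: 0.50 × 0.70 × 15 = 5.25, about 5.3 days.

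**Step 4: effect on the comparison between arms over six months.**
Hidden difference = P(death) × (share in standard arm − share in early-referral arm) × mean terminal stay, with the same stay length in both arms.

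- 50% against 50%: 0.50 × 0 × any length = 0. The level is understated, and the absolute difference is unaffected.
- 60% against 40%, 14-day stays (assumed): 0.50 × 0.20 × 14 = 1.4 days hidden.
- Same case, with one extra day of completed stays in the early-referral arm (assumed): the true difference, standard minus early, is 1.4 − 1.0 = +0.4 days, but the measured difference is −1.0 day. A change of sign is possible, given those inputs.

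**The case against.** The strongest reply is that exclusion is never stated. Section 19.2.2.2 says a number will be reported. It does not say those stays leave the mean or the total, and the same count would include patients still in a bed at the data cut. Section 19.2.2 calls the text an outline with detail to follow in an SAP, which could close terminal stays at death. This stands in part: exclusion is the literal consequence of the definition, not an announced rule. But the protocol does more than stay silent. It fixes the end of a stay at discharge, and an SAP that ended stays at death would have to depart from that.

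A reader might infer several stronger things that the protocol does not support:

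- **That the comparison is biased between arms.** Nothing in the protocol says early referral will change the place of death; section 2.1.3 asks an open question about resource use. Hospital and hospice are pooled, so a move from hospital death to hospice death leaves the number of lost terminal stays unchanged. Bias needs a difference in the combined share or in terminal stay length.
- **That ITU deaths are knowingly set aside.** The count and the test apply to hospital and hospice only. For ITU, the length of a visit ending in death is simply undefined.
- **That the cost-effectiveness result inherits the error.** The days appear under a cost-effectiveness heading, but section 11.2 has its own costing method, using routine records and an adjustment for censoring, and does not adopt this duration rule.
- **That a main result is at risk.** The outcome is secondary; neither co-primary outcome nor the sample size depends on it.

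**Conclusion.** The point holds as a defect in a stated definition. Applied as written, stays ending in death have no duration, and days in hospital or hospice are understated in both arms. The size is about 0.75 to 5.3 days per randomised patient over six months. Of the inputs, the 50% mortality comes from the protocol's own assumption; the 30% to 70% share and the 5 to 15 day stay are assumptions.

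Distortion of the difference between arms is conditional. It arises if the share of deaths in hospital or hospice, or the terminal stay length, differs by arm, and the protocol gives no figures from which to predict its size or direction.

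A reader might prefer the final-analysis horizon, where 0.882 × 0.30 × 5 = 1.3 and 0.882 × 0.70 × 15 = 9.3 days. That adds an assumption of uniform accrual to the two already made. The six-month figure needs only the stated survival assumption and matches the horizon of the quality-adjusted survival outcome, so it is the one to quote.

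This is a modest correction to a secondary outcome, worth making because deaths are frequent and the remedy is simple.

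**What to change.** In section 19.2.1.2, define the duration of hospital, hospice and ITU stays as the time from admission to the earliest of discharge, death or data cut-off. In section 19.2.2.2, state that stays closed by death or by the cut-off are included in the mean and total days compared between arms, and keep reporting how many stays ended in death and how many were ongoing.

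The cost is slightly more data handling, to link each stay to the date of death. Stays are already to be taken from patient records, and the date and place of death are already collected (section 7.2.4). Section 7.2.2.2 lists hospital admissions and their duration on the CRF but does not expressly mention admission dates or hospice and ITU stays, so check that an admission date is recorded for all three settings.

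Totals also depend on how long patients live. A fixed time window, or days alive and out of hospital and hospice, could be added as a supportive analysis. Either is a design preference and is not needed to correct the definition; a six-month window would also leave out the terminal stays of patients who die later.

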19.2.2 Analysis of Outcome Measures

Full details will be specified in a Statistical Analysis Plan but an outline of the planned analyses is provided below.

19.2.2.1 Primary Outcome Measures

Global health status score: The two treatment groups will be compared in terms of this outcome measure at three months using a t-test. It is recognised that there will be some variation in the timing of the QoL assessments and a window of two weeks either side of the planned three month assessment will be acceptable. This part of the analysis will only be carried out in those patients who are alive and well enough to complete a questionnaire at three months (i.e. a complete case analysis) and therefore it is a conditional analysis but it will be intention-to-treat in the sense of including patients under their randomised allocation.

QAS time: Treatment groups will be compared using a t-test. The advantage of this analysis is that it is intention-to-treat, dealing with missing data due to death and dropout and therefore including all randomised patients in the analysis.

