6.2 Randomised Controlled Trial - Randomisation

To randomise a patient into the RCT complete a Randomisation Form and call the CRCTU using the number below.

2 [name]

9.00 am till 5.00 pm Monday to Friday

The CRCTU Randomisation Office will be closed on Bank Holidays and University of Birmingham closed days.

Sites will be informed of forthcoming closures in advance.

The following information should be provided:

- Name of site and investigator
- Patient's initials
- · Date of birth
- · Confirmation of eligibility
- Date of patient consent
- Whether the patient has consented to the optional aspects of the study. If the patient has consented to the Qualitative Interviews their full name and telephone number will be collected)
- Details of carer consent including their initial's, whether they have consented to the qualitative interviews. If the patient has consented to the Qualitative Interviews their full name and telephone number will be collected)

Patients will be randomised using a computerised minimisation technique. Stratification variables include:

- Site
- Age (<50 years, ≥50 year)
- The presence or absence of brain metastases
- mGPS (scores 0, 1 or 2)

Patients will be randomised one-to-one to the following arms:

- Arm A: Standard Care
- · Arm B: Early referral to SPC

Patients allocated to Arm B will undergo a second randomisation (1:1) to:

- Arm B1: Sites Standard SPC
- Arm B2: Sites Standard SPC + SPARC

Patients will be issued with a unique Trial Number which should be used on all correspondence with the Trial Office.

The completed Randomisation Form, Eligibility Checklist and a copy of the Informed Consent Form should be sent to the Trial Office.

With the patient's prior consent their GP should also be informed that they are taking part in the trial. A RCT GP Letter is provided electronically for this purpose.

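### Both co-primary analyses are fixed as unadjusted t-tests, although the minimisation factors and baseline scores are collected; the tests are valid but give up precision that adjustment would recover

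*Protocol*

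**What the plan says.** Protocol section 19.2.2.1 names the test for each co-primary outcome. For GHSS, "The two treatment groups will be compared in terms of this outcome measure at three months using a t-test". That analysis is limited to patients "alive and well enough to complete a questionnaire at three months (i.e. a complete case analysis". For the other outcome, "QAS time: Treatment groups will be compared using a t-test". No covariate is named for either. Section 19.2.2 introduces this as an outline: "Full details will be specified in a Statistical Analysis Plan but an outline of the planned analyses is provided below".

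Four other places bear on the choice:

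- **Allocation (section 6.2).** "Patients will be randomised using a computerised minimisation technique", with site, age (under 50 or 50 and over), brain metastases and mGPS as factors, and a 1:1 ratio between Arms A and B.
- **Baseline data (Appendix 8, Table 3).** The RCT baseline booklet holds EQ-5D-5L and QLQ-C30, so both outcomes have a baseline value.
- **QAS definition (section 19.2.1.1).** QAS is the area under the EQ-5D-5L utility curve over six months, with zero from death onwards.
- **Prognostic variables (section 2.2.2).** Of mGPS and the co-morbidity index, the protocol says that they may influence symptoms, needs and survival, "so will be used in the statistical analysis to help explain variations" in outcomes.

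**The concern.** Minimisation forces the arms to be alike on factors thought to be prognostic. A two-sample t-test does not use that. It leaves the variation due to those factors in the error term, so its standard error is larger than the real sampling variation of the difference between arms. The baseline score is a separate matter. Leaving it out does not make the standard error wrong, but it forgoes whatever part of the outcome the baseline value predicts, and it leaves chance baseline imbalance in the estimate.

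At stake is precision in a trial planned at 80% power that would need up to 700 patients for 90%. The remedy uses data already being collected. It is also better fixed in advance, because covariates chosen after the data are seen invite the charge of selection.

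This is not a detail merely left to the SAP. The protocol names the primary test, and its sample sizes are those of that test.

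**Working it through.** **Inputs from the protocol (section 19.2.5).** Two-sided 5% level. GHSS: difference 7, SD 23, 35% total loss. QAS: difference 0.5 months, SD 2, all randomised patients analysed. Minimum sample 525.

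**Assumed, because the protocol does not give them.** The correlation r between baseline and three-month GHSS; the multiple correlation R of QAS with its covariates; the share of variance R² explained by the minimisation factors.

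**Step 1: the plan's own figures.** The unadjusted two-sample t-test (noncentral t) gives:

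- GHSS, effect 7/23 = 0.304: 342 for 80% power and 456 for 90%, as stated.
- QAS, effect 0.5/2 = 0.25: 506 and 676, as stated.
- Inflation: 342/0.65 = 526 and 456/0.65 = 702, against 525 and 700 stated, within two patients.

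The sample size is therefore that of an unadjusted t-test. With 525 randomised, 525 × 0.65 = 341 are analysed for GHSS.

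**Step 2: gain from a baseline covariate.** The residual SD is SD × √(1 − r²), and the confidence interval shrinks by the same factor. Power is then recomputed at the same numbers.

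| r (or R), assumed | √(1 − r²) | GHSS power, 341 analysed | QAS power, 525 analysed |
|---|---|---|---|
| 0 (planned t-test) | 1.000 | 80.0% | 81.6% |
| 0.2 | 0.980 | 81.6% | 83.1% |
| 0.3 | 0.954 | 83.6% | 85.0% |
| 0.4 | 0.917 | 86.4% | 87.7% |
| 0.5 | 0.866 | 89.9% | 91.0% |
| 0.6 | 0.800 | 93.9% | not claimed |

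**Step 3: effect of leaving out the minimisation factors.** If balance on them is near perfect and they explain R² of the variance, the true variance of the difference is (1 − R²) times what the t-test assumes. The true alpha is then 2 × [1 − Φ(1.96/√(1 − R²))].

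| R², assumed | 1.96/√(1 − R²) | True alpha | Coverage of the nominal 95% interval |
|---|---|---|---|
| 0.05 | 2.011 | 0.044 | 95.6% |
| 0.10 | 2.066 | 0.039 | 96.1% |
| 0.20 | 2.191 | 0.028 | 97.2% |
| 0.30 | 2.343 | 0.019 | 98.1% |

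For GHSS these are outer values, since only about 65% of the minimised patients are analysed and balance in that subset is not guaranteed. Steps 2 and 3 are separate illustrations and should not be added together.

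**Step 4: what missing baselines would cost.** Section 19.1.1 sets a target of 90% completion of baseline GHSS. If patients without a baseline were simply dropped, 0.9 × 341 = 307 would remain. At r = 0.3 power would then be 79.6%, slightly below the 80.0% of the unadjusted test on all 341. The gain therefore depends on a rule that keeps these patients in.

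**The case against.** The strongest reply is that the planned tests are sound: randomisation protects the comparison, type I error is not inflated, and the sample size was derived for exactly these tests. That stands. The point is about efficiency, not validity.

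It is also fair that the size of the gain rests on assumed correlations. At r = 0.2 GHSS power moves by less than two points. A reader might infer that 525 patients would give the 90% power for which the protocol asks 700. That holds only at r of about 0.5 or more, and nothing in the protocol supports a particular value.

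Three further inferences are tempting but not supported:

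- **That both tests ignore the monthly scores.** This is true of GHSS only. QAS is the area under the repeated utilities, so those scores are used.
- **That the intervals are too wide on every count.** Over-coverage follows only from omitting the minimisation factors. Without the baseline score the interval is correct, only less precise.
- **That section 2.2.2 contradicts section 19.2.2.1.** It promises that mGPS and co-morbidity will be used in the statistical analysis, not that the primary comparison is adjusted for them. An unadjusted primary analysis with supporting models would satisfy both sections. What is missing is a link between them.

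Two cautions about the remedy also stand. Section 7.2.2.1 places baseline assessments as soon as possible after trial entry, so in an unblinded trial the baseline booklet may be completed once the arm is known. And a mixed model on all GHSS scores up to three months would implicitly extrapolate scores for patients who have died, unless it is restricted to those alive at three months.

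**Conclusion.** The point holds as a specific improvement to a stated method. Section 19.2.2.1 fixes unadjusted t-tests for both co-primaries while the design balances on four factors and collects baseline values of both outcomes. The consequences are conservative intervals (true alpha about 0.044 to 0.019 for an assumed R² of 0.05 to 0.30 with near-perfect balance) and forgone power: GHSS from 80% to 82–94% for an assumed r of 0.2 to 0.6, and QAS from 82% to 83–91% for an assumed R of 0.2 to 0.5.

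That the tests are unadjusted, and that the sample sizes rest on them, is certain from the text. How much is lost is not, since none of the correlations is in the protocol. The change is worth making, but the trial's validity does not depend on it.

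**What to change.** In section 19.2.2.1:

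1. Make the primary analysis of each co-primary a linear regression on arm, the baseline value of the outcome (GHSS, or EQ-5D-5L utility for QAS) and the minimisation factors: site, age, brain metastases and mGPS.
2. State a simple rule for missing baselines, such as mean imputation or a missing indicator, so that no randomised patient is dropped for that reason.
3. Enter baseline scores as covariates only if the booklet is completed before allocation is known. The minimisation factors are available regardless, since they are needed for allocation and section 7.2.2 requires mGPS before randomisation.
4. Keep the t-tests as sensitivity analyses.
5. Add a sentence linking section 2.2.2's statement on mGPS and co-morbidity to this model.
6. Optionally, add a repeated-measures model for GHSS as a sensitivity analysis for living patients who miss the month-three booklet, restricted to patients alive at three months.

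The cost is protocol and SAP wording and slightly more analysis work, with no new data items. The estimate becomes model-based. If baseline scores are to be used, sites must also have the booklet completed before randomisation.
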